Study efficacy will be determined by comparing the rates of hospitalizations and ER visits between intervention and control study site veteran organ transplant recipients, while adjusting for baseline patient, provider and facility characteristics. Secondary measures include comparing estimated healthcare costs and determining dashboard functionality, dashboard actionability and pharmacist intervention types and acceptance rates. We will also assess the overall incidence and severity of drug-related problems and graft and patient survival rates and compare these between the intervention and control sites.

Interventions and Duration

The study will randomize 10 sites to usual care or usual care plus intervention in a parallel arm design and study duration will be 24-months.

The intervention will include a pharmacist that utilized a dashboard system to identify veteran organ transplant recipients with the potential of immunosuppressant medication-safety issues. The technology component of this intervention consists of the use of a dashboard system that performs population-level surveillance of organ transplant recipients and identifies those with potential drug-related problems, including non-adherence to immunosuppression medications, drug interactions, missing and worrisome trends in labs and recent hospitalizations and ED visits; then providing a real-time alert to the pharmacist, who will determine its relevance and intervene in an appropriate protocol-guided manner.

Sample Size and Population

There will be 10 sites included in this study with an estimated average of 169 veterans per site, totaling 1,689 veterans across the entire study population, divided approximately equally between the intervention and usual care groups

The patient population will consist of veterans that received solid organ transplants (kidney, liver, pancreas, heart, or lung) and receive their immunosuppression medications through the VA system. Patients will be identified using ICD-9 or 10 codes and VA medication prescription information.

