- We completed an interrupted time series analysis, demonstrating significantly improved adherence to appropriate immunosuppression laboratory monitoring by using a population surveillance dashboard to identify Veteran transplant recipients with missing laboratory data, allowing the pharmacist to efficiently intervene by engaging the Veterans to either schedule labs or document non-VA care. Using segmented regression, we demonstrated a 38% improvement in monitoring ($p<0.001$), at a rate of 4.7% improvement per month for the first six months of the intervention ($p<0.001$).¹⁸ Thus, we have strong preliminary data that the dashboard is functional and can be an effective instrument to identify Veterans needing attention in a time-sensitive and efficient manner. This dashboard system is currently being utilized at multiple sites (one in VISN 7 and several in VISN 12). For this proposal, we plan to expand the dashboards functionality and incorporate its use by pharmacists as part of clinical care at the 5 sites randomized to the intervention arm of this study.

The cluster-randomized design of this study was chosen for a number of important reasons. First, this study design will allow investigators to test a promising intervention against a similar control group with respect to patient constitution and time. The use of randomization at the site level will allow us to complete the 24-month study within a reasonable period and within the budget constraints. Using the cluster randomized parallel design at 10 sites will provide sufficient patient numbers to meet statistical power to detect clinically meaningful differences in health care utilization.

Randomization at the patient-level, as opposed to the site, would not be feasible, as there would be a high probability of cross-contamination based on the intervention proposed and the technology component, which uses site-specific population surveillance. Additionally, randomization at the patient-level would substantially prolong enrollment, thus making completion within 4 years infeasible. Other trial designs were considered and discussed with the investigational group, including stepped-wedge, interrupted time series, one group pre-post test, one group post-test only and a

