4.3 Study Enrollment Procedures

Once IRB approval is obtained (via central IRB), each potential participating pharmacist will undergo informed written consent. Following this, each site will be randomized to

standard care or standard care plus the pharmacist-led intervention. To ensure a roughly equal number of patients between the two comparison groups, randomization will be stratified by estimates veteran organ transplant recipients (<125 versus ≥ 125 active patients). After randomization, each participating pharmacist will be informed of their assigned group. Those in the intervention arm will be trained on the dashboard system, utilizing the dashboard, and delivering the intervention. Those in the usual care group will continue to provide the same level of care they are currently providing as part of their normal day-to-day activities and job functions.

If a site or participating pharmacist withdraws prior to study initiation, if possible, it will be replaced with a suitable alternative site/pharmacist. If a site pharmacist withdraws after initiation, the investigational team will determine if the site needs to be replaced. This will depend on how far along the intervention is and the number of veterans impacted by the withdrawal.

Because this is a cluster-randomized trial, and randomization occurs at the site level, we will not recruit, consent, or enroll at the subject level. We will request waiver of written documentation of patient informed consent. We request waiver of HIPAA for all patients.

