9.2 Sample Size and Randomization

Based on the projected enrollment numbers, there is ample power to detect a statistically significant difference between the intervention and control groups with regards to the primary aim of hospitalization and ED visit rates. To determine this, we used data from a recent national study conducted between 2009-2012.⁵³ These results demonstrated that the rate of ED visits after transplant was 1.269 per person-year and 48% of those ED visits resulted in hospitalization. We will enroll 10 sites (5 sites for each study arm) and will have a total of just more than 1,600 patients that are roughly split between the intervention and control sites. We used a conservative estimate of an intra-cluster correlation of 0.05 and calculated a sample size of 1,350 to allow us to detect a 25% relative decrease in ED visit and hospitalization rates with 80% power. The 25% relative improvement in rates is a conservative estimate of intervention effect, based on previous pharmacist-led initiatives the investigators have conducted.^{15,16} After allowing for 15% loss to follow up, we require a total of 1,600 to meet study power. We expect to have 1,689 patients based on site estimates. These power calculations were conducted using a two-sided test for counts with Poisson regression adjusting for intra-cluster correlation and with alpha set at 0.05.

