9.2.1 Treatment Assignment Procedures

Randomization will occur at the site level (cluster randomized trial). Ten sites will be randomized to either the intervention arm or usual care arm using statistical software (SAS, SAS Institute, Cary, NC). Randomized will occur after all sites have agreed to participate and site-level regulatory approval has occurred. Randomization will be stratified by site using estimated sample size (<125 vs. ≥ 125 veteran organ transplant recipients). This will be done to ensure an approximate even distribution of patients across study arms.

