9.4 Data Analyses

The data analysis will incorporate the intent-to-treat principle; namely, all participants enrolled in the intervention group will be included in the analysis and compared to all of the patients captured within the control group. If a patient dies, has graft loss or moves out of their study site, their data will be censored at that time point. For comparative statistical assessments within the utilization outcomes, the two groups will be compared using a generalized linear mixed models (GLMM) approach.⁵⁴ This approach allows for measurement of participants at different time points, clustering by study site, missing data under the assumption of missing at random (MAR), time varying or invariant covariates, and can also account for the effect of correlated longitudinal measurements within participants. In addition, GLMM accommodates a wide range of distributional assumptions such as dichotomous (e.g. binomial), count (e.g. Poisson), continuous

(e.g. Gaussian), and categorical or ordinal outcomes. For comparing the primary outcome (ED visit and hospitalization rates), we will use GLMM (with appropriate link function) with counts of these events as the outcome variable and intervention group (yes/no) as the primary independent variable. This analysis is equivalent to Poisson regression or negative binomial regression (in the case of over-dispersion), both special cases of GLMM. Additional adjustment covariables will be added to the model in a second set of analyses. Covariates will include patient sociodemographics: age, sex, race, comorbidities (using modified Elixhauser definitions), marital status and education. In these models, donor information (age, sex, race, deceased or living) and transplant characteristics (HLA mismatches, ischemic times, panel reactive antibody levels, time since transplant) will also be included. This will assist in making valid intervention effect estimates after accounting for baseline differences, as there may be patient-level differences between groups. The magnitude of between intervention differences on outcome variables (effect sizes) at each time point will be estimated using appropriate contrasts in the corresponding GLMM models.

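### The ten sites are allocated with a single two-level size stratum, so baseline encounter rate is controlled neither in the draw nor in the primary model; a constrained draw plus adjustment for prior site rate would recover precision cheaply.

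*Combined protocol and SAP*

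**What the plan says.** **Aim of the design.** Section 2.2, repeated in 9.1, gives as a reason for cluster randomisation that it will "test a promising intervention against a similar control group with respect to patient constitution and time". The synopsis (Sample Size and Population) expects 1,689 patients, about 169 per site, "divided approximately equally between the intervention and usual care groups".

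**Allocation.** Section 9.2.1: "Randomization will be stratified by site using estimated sample size", with one cut at 125 recipients. The stated purpose is numbers only: "This will be done to ensure an approximate even distribution of patients across study arms" in 9.2.1, and "To ensure a roughly equal number of patients between the two comparison groups" in 4.3. Randomisation follows agreement and regulatory approval of all sites, so all ten are known beforehand.

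**Analysis.** The first primary model in 9.4 has intervention group as its main predictor. Covariates enter in a second set of analyses, "as there may be patient-level differences between groups". The list covers demographics, comorbidities, donor and transplant characteristics. It has no prior utilisation and no facility or provider variable, although the synopsis (Design and Outcomes) promises adjustment at patient, provider and facility level.

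**Data.** Section 10.1 names the VA data warehouse (CDW) as the source for admissions and ER visits. Sections 9.3.2 and 9.4 already plan to use costs from the two years before the study. Non-VA encounters come from Medicare linkage after study completion (9.3.1).

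**The concern.** With five sites against five, randomisation makes the arms alike on average over draws, but not in the one draw that will be used. Section 5.3 says usual care varies across the ten sites. Differences between sites in their usual encounter rate dominate the error of this comparison, while patient numbers hardly affect it. The plan spends its only allocation restriction on patient numbers and leaves the larger source of error to chance. At stake is the precision of the primary rate ratio, and whether readers accept the control arm as similar if the arms start from visibly different rates. The allocation part can be changed only before randomisation.

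**Working it through.** **1. The plan's sample size (9.2).** Inputs: 1.269 ED visits per person-year, 24 months, 25% reduction, two-sided alpha 0.05, 80% power, ICC 0.05, ten sites. Two-year means are 2 × 1.269 = 2.538 and 0.75 × 2.538 = 1.9035. With 1,350/10 = 135 per site, the design effect is 1 + 134 × 0.05 = 7.7.
- Log-ratio form: n per arm = (1.96 + 0.84)² × (1/2.538 + 1/1.9035) / (ln 0.75)² = 87.2. Total 2 × 87.2 × 7.7 ≈ 1,343.
- Rate-difference form: 86.6 per arm, total about 1,334.
- Loss to follow-up: 1,350/0.85 = 1,589.

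The plan's 1,350 and 1,600 are reproduced closely.

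**2. What patient numbers buy.** In the log-ratio form with a normal reference, power is 80.2% at 1,350 and 81.2% at 1,689. A 55:45 split keeps 4 × 0.55 × 0.45 = 99% of patient-level efficiency; 60:40 keeps 96%.

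**3. What site mix costs.** With Poisson variation within sites:
- Between-site variance = (0.05/0.95) × 2.538 = 0.1336; SD 0.365; CV 0.365/2.538 = 14.4%.
- SD of the log rate ratio between arms = 0.144 × √(2/5) = 0.091; 95% range 0.84 to 1.20.
- Ratio beyond 10% either way: ln 1.10/0.091 = 1.05 SD, about 30% of draws.
- At least half the planned effect (12.5%): about 17%.
- A 25% reduction: |ln 0.75|/0.091 = 3.2 SD, about 0.2%.

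**4. What the size stratum does.** The documents give no individual site sizes. The 252 allocations were enumerated with assumed size CVs of 0.3/0.5/0.7.
- Average larger-arm share: 53/55/57%.
- Larger arm above 60% of patients: 1/9/22% of draws.
- A site characteristic unrelated to size differs by more than half a site SD in 46% of draws, the same as with no stratum. Keeping the best 25% of allocations on size plus three site characteristics cuts this to 19%. A characteristic left out of the constraint stays at 46%.

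**5. What a constrained draw on prior rate and size does.** With 63 of 252 allocations kept, the 30% of draws differing by more than 10% falls to about 24%, 19% or 6% for assumed correlations of 0.5, 0.7 or 0.9 between prior and study-period site rates.

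**6. What reaches the test.** Simulated power for a 25% effect, using a t-test on site log rates with 50 allocations kept:

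| Draw and analysis | r = 0.5 | r = 0.7 | r = 0.9 |
|---|---|---|---|
| Simple, unadjusted | 74% | 74% | 74% |
| Constrained, unadjusted | 74% | 75% | 77% |
| Simple, adjusted for prior rate | 77% | 87% | 99% |
| Constrained, adjusted for prior rate | 81% | 91% | 99.6% |

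A separate enumeration gave about 72% unadjusted, rising to 79–81%, 89–91% and 99% with constraint plus adjustment, and type I error near 5%. The constrained draw tested without adjustment is conservative: type I error about 3.5%, 2% and 0.5%.

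An analytic check uses the inflation factor 0.95 + 0.05 × 135 × (1 − R²), where R² is the assumed share of between-site variance explained. This gives 7.70 at R² = 0, 6.01 at 0.25 and 4.33 at 0.50. Rate-difference power at 1,350 is then about 70% (t, 8 df), 78% and 89% (t, 7 df).

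**7. How tight the constraint may be.** The smallest two-sided permutation p is 2 divided by the number of allocations kept: 2/25 = 0.08, 2/40 = 0.05, 2/50 = 0.04, 2/63 = 0.032.

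**The case against.** Random allocation of sites is unbiased, and the site variance in step 3 is derived from the same ICC that 9.2 builds into the sample size and that 9.4 models as clustering. That stands: this is a matter of efficiency. A reader might infer that one unlucky draw could mimic the planned 25% effect. At 3.2 SD it is too improbable to argue from.

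A reader might also infer that the stratum fails to deliver the promised split. The plan promises only a roughly equal one, site sizes are not given, and moderate inequality costs little, so failure on size is not shown.

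The similar-control-group statement is a reason for choosing the design over alternatives such as pre-post, not a claim about the stratum. That is fair. It still means that no allocation step supports the statement beyond chance.

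Section 9.4 does adjust for case mix, and patient-level covariates are estimated largely within sites on some 1,600 patients. That stands too, but this adjustment is secondary and lists no prior utilisation.

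The strongest objection is that most of the gain comes from adjustment. Changing the draw alone gains almost no power and makes the test conservative. This is correct, and it is why the fix has two halves.

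**Conclusion.** The point holds as a cheap improvement that should be made before the draw, not as an error that invalidates the trial. The stratum leaves baseline encounter rate and case mix to chance, and the first primary model does not take up prior rate. The cost is a log rate ratio SD of about 0.09 from site mix, and power nearer 70% to 74% than 80% when site-level degrees of freedom are respected. Constraint plus adjustment recovers that loss to a degree set by how well prior VA rates predict study-period rates.

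That correlation is assumed. The low end may apply, because section 2.2 puts dual users at nearly two-thirds and VA rates miss non-VA encounters. Other assumptions are Poisson variation within sites (with overdispersion, an ICC of 0.05 implies larger site differences), the ED-visit rate standing in for the primary outcome as in 9.2, and the assumed site sizes. The documents do not support a claim that the change removes imbalance or comes free.

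**What to change.** **Sections 4.3 and 9.2.1.** Replace the size stratum by constrained randomisation. From the CDW, compute each site's prior ER-visit and admission rate and its number of recipients. Score all 252 5:5 allocations on these two variables with prespecified weights. Keep about 63 (25%), and never fewer than 40. Mirror-image allocations score equally, so 62 or 64 in practice. Check that no two sites are always or never together, draw one allocation at random, and file the score. State that balance is rescored and documented if a site is replaced under 4.3.

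**Section 9.4.** Put prior site encounter rate in the primary model, with small-sample site-level degrees of freedom. Do not add several site-level terms: at correlation 0.5, adjusting for three gave 72% power, below the simple unadjusted 74%.

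**Costs to state.**
- One baseline query and a short program.
- One site-level degree of freedom.
- A smaller randomisation set: the present stratum allows 120 to 252 allocations, depending on how many sites fall below 125.
- Prior rates that miss non-VA encounters until the Medicare linkage, so the gain may be modest.
- Imbalance that is reduced, not removed, with no gain for variables left out of the constraint.
- Site replacement that can undo the balance.

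No extra sites or patients are needed. If sites have already been drawn, the change to 9.4 is still available and carries most of the power gain.

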3 STUDY DESIGN

[figure not shown]
This is a 24-month prospective, parallel arm, cluster-randomized, controlled multicenter study in veteran organ transplant recipients receiving immunosuppressant medications through the VA system. The trial will randomize 10 VA sites, 5 to standard of care and 5 to standard of care plus the intervention. The intervention consists of a pharmacist-led health services endeavor utilizing a transplant medication dashboard system that monitors and reports on potential immunosuppression-related safety issues. The study will use prospective methodology to monitor patients for 24-months following site-randomization, comparing outcomes between the intervention and control sites. Clinical outcomes that will be assessed include health care encounters (hospitalizations and ER visits), estimated health care costs, and graft and patient survival. The functionality of the dashboard system will also be assessed by analyzing the proportion of actionable alerts created by the system as well as the proportion of missing labs, proportion of alarming lab values without follow up scheduled, estimated immunosuppression adherence (using the proportion of days covered [PDC]), proportion of significant drug interactions without an immunosuppressant level and the proportion of hospital and ER visits without follow up.

The study population will consist of veteran organ transplant recipients that receive immunosuppressant medications through the VA system. Organ transplant recipients will be identified using ICD-9/10 codes from the VA electronic health record. Once identified, active medications will be queried and those receiving immunosuppressant medications to prevent rejection (tacrolimus, cyclosporine, azathioprine, mycophenolate, sirolimus, everolimus, or belatacept) will be included in the study.

The study will take place at 10 VA sites, with 5 being randomized 5 to standard of care and 5 to standard of care plus the intervention. The 10 site locations are listed in the participating sites section of this protocol. After randomization and site initiation, all intervention sites will go live on the dashboard and pharmacist-led intervention simultaneously. Following this, patients at both the intervention and standard of care sites will be prospectively monitored for 24 months, in a parallel fashion.

The sites randomized to the intervention arm will continue to use current standard of care procedures within their sites, while also utilizing the dashboard system daily to identify veteran transplant recipients with potential medication safety issues. Each day, the pharmacists will open the dashboard system, which is updated at approximately 7:00 AM each morning. The system will identify new patient-specific alerts that will inform the pharmacist on potential medication safety issues. The pharmacist will then serve as a patient navigator, intervening to resolve the medication safety issue, by using

detailed protocols within the standard operating procedure (SOP) manual that the pharmacists will be trained on prior to study initiation. Once the pharmacist validates that the dashboard alert is a relevant issue, they will develop a management plan using these protocols (Figure above), discuss the recommendations with the providers (when necessary), agree on a plan, and implement the plan. The primary medication safety issues the intervention pharmacists will be alerted to, and address are laboratory abnormalities, medication non-adherence, drug interactions and medication

coordination/communication issues. For laboratory abnormalities, common issues encountered within transplant patients include electrolyte irregularities, organ dysfunction, drug level outliers and cytopenias. For each of the laboratory values that will be monitored and reported in the dashboard, a detailed algorithm in the standard operating procedures (SOP) manual delineating how to address the issues will be used for the pharmacist-led intervention. For instance, it is well known that magnesium levels are low in transplant recipients due to a side effect of calcineurin inhibitors.⁵⁰ Strategies to address this include dietary interventions and supplementation. Issues with out-of-range drug levels will also be addressed. These include ensuring the patient is taking the correct dose, ensuring the level is a true trough value, checking for new drug interactions and adjusting the dose when necessary. When medication non-adherence is identified as a potential issue, the pharmacist will determine if it is deliberate or unintentional. Strategies to address deliberate non-adherence include removing

perceived or actual barriers, using motivational interviewing, and addressing side effects and cost issues. For unintentional non-adherence, pharmacists can implement trigger reminder strategies, simplify regimens, and re-educate. Within drug-interaction alerts, the intervention will focus on reducing the impact of these through changing of regimens (when appropriate), educating patients and/or providers and increased monitoring and surveillance.⁵¹ Alerts for medication coordination issues will encompass discharges from the ER and hospital and missed laboratory assessments. The intervention pharmacist will ensure accurate and safe medication regimens through medication reconciliation and improved medication safety surveillance through the scheduling and follow up of laboratory assessments.¹⁷ To ensure fidelity across sites and efficiency for providers, the specific day-to-day tasks involved with this intervention, which include assessing and intervening on the alerts and appropriate follow up with patient and providers, will be delivered using the SOP manual.¹⁵⁻¹⁷

